3.0 SELECTION AND WITHDRAWAL OF SUBJECTS

3.1 INCLUSION CRITERIA

All subjects are required to meet the following inclusion criteria in order to be considered eligible for participation in this trial:

General Inclusion Criteria

1. Age > 18 and ≤ 90 years of age.
2. Willing and able to provide informed consent.
3. Subject is willing to undergo all follow-up assessments according to the specified schedule over 36 months.

Clinical Inclusion Criteria

4. Chronic, symptomatic lower limb ischemia defined as Rutherford clinical categories 3, 4, or 5.
5. Venous Clinical Severity Score < 3.
6. Subject is a suitable candidate for angiography and endovascular intervention and, if required, is eligible for standard surgical repair.

Angiographic Inclusion Criteria

7. Symptomatic femoropopliteal chronic total occlusions ≥ 20 cm (TASC D) that can include de novo, restenotic, or in-stent restenotic lesions; *or*
Symptomatic femoropopliteal lesions ≥ 24 cm (total lesion length) that can include a chronic total occlusion or a ≥70% lesion that includes de novo, restenotic or in-stent restenosis (complex TASC C), by investigator visual assessment.
8. Reference vessel diameter ≥ 4.5 and ≤ 6.7 mm, by investigator visual assessment.
9. Subject has a patent popliteal artery (<50% stenosis) distal to the landing zone

10. Able to successfully access the SFA origin for entry of the crossing device.
11. At least one patent infrapopliteal vessel (<50% stenosis) with run-off to the ankle or foot.
12. A significant stenosis ($\geq 50\%$) or occlusion of an ipsilateral, inflow artery (e.g. aortoiliac, common femoral) must be successfully treated (use of investigational treatment prohibited) prior to treatment of the target lesion. Successful treatment is defined as no complications and less than 30% residual stenosis following intervention.

3.2 EXCLUSION CRITERIA

Subjects will be excluded from participating in this trial if they meet any of the following exclusion criteria:

General Exclusion Criteria

1. Participating in another investigational clinical study.
2. Anticipated life expectancy less than 1 year or medical comorbid condition(s) that could limit the subject's ability to comply with the requirements of the trial.
3. Subject has other medical, social or psychological problems that, in the opinion of the investigator, preclude them from receiving this treatment, and the procedures and evaluations pre- and post-treatment.

Clinical Exclusion Criteria

4. History of deep vein thrombosis on either limb.
5. Thrombophlebitis, within the previous 30 days.
6. Planned amputation of the target limb, including minor amputation.
7. Prior distal amputation (above the transmetatarsal) of the target limb.
8. Known or suspected active infection at the time of the procedure (e.g., WIFL foot infection grade 3: Severe infection. Local infection with systemic inflammatory response syndrome [SIRS]).
9. Rutherford clinical category 0, 1, 2 or 6.
10. Has acute or chronic renal disease with GFR ≤ 30 ml/min per 1.73 m^2 and/or elevated serum creatinine $>2.5\text{mg/dL}$ ($220\mu\text{mol/L}$) or on dialysis.

11. Known hypersensitivity/allergy to the investigational devices and/or required pharmacotherapy that cannot be safely managed.
12. Morbid obesity that does not allow for safe vascular access or imaging.
13. Subject has a known coagulopathy or has bleeding diatheses, thrombocytopenia with platelet count less than 100,000/microliter or INR > 1.8.
14. Requires coronary or peripheral procedure within 30 days prior to or planned within 30 days post treatment of the target lesion.
15. Has a known history of intracranial bleeding or aneurysm, myocardial infarction or stroke within the last 3 months.
16. Subject is pregnant or breast-feeding.

Angiographic Exclusion Criteria

17. Stent within 3 cm of SFA ostium.
18. Previous bypass surgery on the target limb.
19. Subject has significant disease or obstruction ($\geq 50\%$) of the inflow tract that has not been successfully treated at the time of the index procedure (success measured as $\leq 30\%$ residual stenosis, without complication)
20. Presence of aneurysm or acute thrombus in the target limb.
21. Thrombolysis of the target vessel within 72 hours prior to the index procedure, where complete resolution of the thrombus was not achieved.

3.3 WITHDRAWAL OF SUBJECTS

Each subject may voluntarily withdraw his/her participation from the study at any time without jeopardy or prejudice. If a subject prematurely terminates from the study, the reason for study termination will be recorded and the results will be tabulated by number and percent for each category. If termination is a result of an adverse event or death, an Adverse Event Form will also be completed. Subjects who withdraw consent after treatment will have their data evaluated until the time of their withdrawal.

The Investigator should follow all unresolved serious adverse events until the events are resolved, the subject is lost to follow-up, the subject has withdrawn consent, the subject completes the study, or the adverse event is otherwise explained.

All reasonable efforts will be made to obtain complete data for all subjects; however, missing observations will occur due to loss to follow-up, withdrawal, or non-adherence with required assessments. Three attempts shall be made to contact subjects who do not return for study follow-up visits. The final attempt shall include a certified letter to the subject regarding study participation. If these subjects cannot be located at the final scheduled visit, they will be considered lost to follow-up. If they are contacted but refuse to return for visits, they will be considered withdrawals. Subjects shall be encouraged to complete a final study exit visit at the time of withdrawal to assess for safety. Data collected up to the time of loss to follow-up or withdrawal will be maintained in the study database and used for analysis purposes, as appropriate. These subjects will not be replaced.

4.0 TRIAL DESIGN

4.1 DESCRIPTION OF TRIAL DESIGN

Prospective, single-arm, multi-center, international clinical investigation to evaluate the safety and effectiveness of the PQ Bypass System to access, deliver guidewires, and implant stent grafts for a percutaneous femoropopliteal (fem-pop) bypass.

4.2 TRIAL ENDPOINTS

4.2.1 Primary Effectiveness Endpoint

The absence of clinically-driven target lesion revascularization and absence of recurrent target lesion diameter stenosis >50% by imaging (e.g., duplex ultrasound (peak systolic velocity ratio of

>2.5) or invasive angiography) with the stent or immediately 1 cm above or below the treated segment. When both modalities are available, angiography takes precedence..

4.2.2 Primary Safety Endpoint

Freedom from a major adverse event (MAE) at 30 days post-procedure defined as any occurrence of the following events: Death, Clinically-Driven Target Lesion Revascularization (CD-TLR), Amputation of the Treated Limb, Symptomatic Deep Vein Thrombosis (DVT), Pulmonary Embolism, or procedure-related bleeding requiring any transfusion of packed red blood cells or surgery.

4.2.3 Secondary Endpoints

1. Major Adverse Events (MAE) at 6, 12, 24 and 36 months
2. Major Adverse Limb Event (MALE) defined as above-ankle amputation or major reintervention including placement of a new bypass graft, interposition graft, thrombectomy, or thrombolysis
3. Major bleeding is defined as any bleeding event requiring transfusion of ≥ 2 units packed red blood cells (PRBC) or surgical repair through 30 days
4. Symptomatic Deep Vein Thrombosis (DVT) on ipsilateral limb at 30 days and 6, 12, 24 and 36 months
5. Pulmonary embolism at 30 days and 6, 12, 24 and 36 months
6. Perioperative myocardial infarctions through 30 days
7. Hematoma ≥ 8 cm related to the device or procedure through 30 days
8. The combined rate of death, target lesion revascularization (TLR), index limb amputation, and an increase in Rutherford Clinical ~~Becker~~ Classification by 2 classes (comparing pre- to post-procedural assessments) at 30 days and 6, 12, 24 and 36 months
9. Stent graft separation and migration identified via ultrasound imaging at 30 days and 6, 12, 24 and 36 months
10. Stent graft separation and migration identified via X-ray at 12 months
11. Stent graft fracture identified via X-ray at 12 months

12. Technical Success defined as successful delivery of the investigational devices to the identified area and removal of delivery system
13. Procedural Success defined as successful delivery of the investigational devices to the identified area and removal of delivery system in the absence of in-hospital MAEs
14. Clinical Success defined as limb ischemia improvement as assessed by Rutherford Clinical Classification (improvement in scale by ≥ 1) at 30 days and 6, 12, 24 and 36 months
15. Limb ischemia by Rutherford Clinical - Classification through follow-up at 30 days and 6, 12, 24 and 36 months
16. Primary Patency at 30 days and 6, 24 and 36 months
17. Primary assisted patency defined as revascularization of non-occlusive (<99%) stenosis within the stent graft or immediately above or below the treated arterial segment with less than 50% residual stenosis at 30 days and 6, 12, 24 and 36 months
18. Secondary patency defined as: revascularization of occlusion (100%) within the stent graft or immediately above or below the treated arterial segment with less than 50% residual stenosis at 30 days and 6, 12, 24 and 36 months
19. Target Vessel Revascularization defined as any repeat percutaneous intervention or surgical bypass of any segment of the target vessel at 30 days, 6, 12, 24 and 36 months
20. Ankle-Brachial Index (ABI) or Toe Brachial Index (TBI) of both the index limb and contralateral limb at 30 days and 6, 12, 24 and 36 months
21. Number of major index limb amputations at 30 days and 6, 12, 24 and 36 months
22. Major procedure-related infections within 30 days
23. Length of post-procedure hospital stay
24. Length of ICU stay
25. Hospital re-admissions through 30 days
26. Change from baseline in VascuQol QOL Score at 30 days and 12 months

27. Change from baseline in EQ-5D-5L QOL Score at 30 days and 12 months
28. Change from baseline in Duplex Venous Observation Scale at 30 days and 6, 12, 24 and 36 months
29. Change from baseline in Villalta and Venous Clinical Severity (VCSS) Scales at 30 days and 6, 12, 24 and 36 months
30. SF-12 Score at Baseline, 30 days and 12 months

4.2.4 Health Economics Analysis

Health care costs and incremental cost-effectiveness for the study population will be assessed throughout through 12 months. The following data elements will be collected for each study subject.

1. Quality-of-life outcome measures will be collected at Baseline, 30 days and 12 months from date of enrollment utilizing the EQ-5D-5L questionnaire
2. Procedure and follow-up cost data, including rehospitalizations, will be collected through 12 months from the date of enrollment.
3. Length of post-procedure hospital stay
4. Length of ICU stay

Follow-up resource utilization and cost data will be collected through 12 months from the date of enrollment. Data to be collected may include, but are not limited to copies of the subjects' hospital bills (UB04) and/or itemized hospital bills. The following personal health information from the UB04 may be collected but not limited to:

1. Subject's hospital admission date
2. Number of devices used
3. Subject's hospital discharge date
4. Subject's procedure date
5. ICD-10 diagnosis and procedure codes, HCPCS and CPT codes
6. Itemized and total charges for hospitalizations
7. Number and duration of admissions to rehabilitation hospitals, nursing homes and other chronic care facilities (and whether the admission was related to PAD and its treatment)

8. Self-reported measures of outpatient medical resource utilization over the course of the follow-up period

4.2.5 Subgroup Analysis

A multivariate logistic regression model will be fit with independent variables (unique for safety and effectiveness analyses) for the subgroup levels as well as the baseline characteristics. Separate baseline characteristics will be developed for safety and effectiveness analyses.

With respect to the primary safety endpoint, the following baseline characteristics will be compared across the subgroups:

- Age (years)
- Gender
- History of smoking
- History of diabetes
- Previous peripheral interventions
- Renal insufficiency
- Congestive heart failure
- Lesion length (cm)
- TASC II classification
- Rutherford classification
- Number of run-off vessels

With respect to the primary effectiveness endpoint, the following baseline characteristics will be compared across the subgroups:

- Gender
- History of smoking
- History of diabetes
- Previous peripheral interventions
- Lesion length (cm)
- TASC II classification
- Rutherford clinical classification
- Number of run-off vessels

Any differences that persist after this adjustment will require further investigation to understand the underlying cause for the observed differences.

4.2.6 Additional Analyses

1. 6 Minute Walk Test at Baseline, 30 days and 12 months
2. Comparison the Open Bypass Primary Patency (Flow vs. No-Flow) at 12 months

4.3 SAMPLE SIZE

Up to 202 subjects, excluding elective roll-ins, with atherosclerotic lesions of the native superficial femoral artery (SFA) or the superficial femoral and proximal popliteal arteries, suitable for treatment with PQ Bypass System will be enrolled.

At least 50% of subjects will be enrolled in the U.S. and no single site will enroll greater than 20% of all subjects.

The first two Subjects enrolled and treated at each site may be considered roll-in subjects. Roll-in subjects will be pre-specified.

4.4 INVESTIGATIONAL SITES

The clinical trial will be conducted at up to 40 clinical sites in the United States and up to 10 sites in Europe.

A single investigational site shall not enroll more than 20% of the total planned trial population (i.e., 42 subjects) without the prior written approval of the Sponsor.

4.5 DURATION OF SUBJECT PARTICIPATION

Subjects enrolled in the trial will participate for approximately 36 months (3 years).

4.6 EARLY STUDY TERMINATION

PQ Bypass reserves the right to terminate the study at any time, but intends only to exercise this right for valid scientific or administrative reasons related to protection of subjects. Investigators and associated EC and CA will be notified in writing in the event of termination.

Possible reasons for study termination include:

- The discovery of an unexpected, significant, or unacceptable risk to the subjects enrolled in the study

- A decision on the part of PQ Bypass to suspend or discontinue development of the device

4.7 WRITTEN INFORMED CONSENT

Subjects who meet general and clinical entry criteria will be asked to sign the study specific Ethics Committee (EC) or Institutional Review Board (IRB) approved Informed Consent Form(s) (**Appendix I**) before any study-specific tests or procedures are performed. Study personnel should explain that even if a subject agrees to participate in the study and signs an Informed Consent Form, the subject may not be eligible to participate if he/she fails screening criteria.

4.8 ENROLLMENT

According to ISO 14155:2011, enrollment in the study occurs at the time of informed consent; however, for the purposes of this study, only subjects who are consented and meet all the study inclusion criteria and none of the study exclusion criteria, venous and arterial access has been achieved and study device advanced beyond the sheath will be considered enrolled into the study. Therefore, the enrollment date (Day 0) will be the date of the study index procedure; the enrollment date will not be the date of informed consent for this study. Subjects in whom the PQ Bypass System is inserted into the vascular and/or the procedure was aborted without treatment with the device shall be followed through discharge for safety only and allowed to exit the study.

Investigators will access the target artery and the corresponding ipsilateral vein using standard percutaneous techniques and devices. Patient eligibility will be confirmed prior to insertion of the study device, based on procedural angiogram and sheath placement.

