7.2.2. Intention to Treat (ITT)

The ITT Cohort includes all subjects enrolled in the IDE Study. The ITT Cohort will be the primary analysis population to determine if the primary safety endpoint was met in the study.

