7.3.1. Missing Data

Subjects free from clinically-driven target lesion revascularization within the stented segment but do not have sufficient follow-up to assess the primary effectiveness endpoint will be treated as having missing data for the primary effectiveness endpoint. To further evaluate the impact of missing data on the primary

effectiveness endpoint, Kaplan-Meier methods, will also be used to estimate the 12-month primary patency rate.

For the primary safety endpoint analysis, the denominator for each parameter in the safety measures will be the number of subjects who had sufficient follow up (at least 23 days for 30-day visit) plus any subjects who had an event prior to the milestone visit.

All subjects will be accounted for in the study report, including the reasons for any subjects exiting the study early.

Every effort will be made to collect all data points contributing to the primary effectiveness endpoint in the study. The sponsor attempts to minimize the amount of missing data by appropriate management of the prospective clinical trial, proper screening of study subjects, and training of participating investigators, monitors and study coordinators. In order to further assess the potential impact of missing data on the primary effectiveness endpoint analyses, the following sensitivity analyses will be performed:

- Worst-Case Scenario: Each missing value for the primary effectiveness endpoint will be treated as a failure. If this still results in rejection of the null hypothesis then no further missing data imputation analyses will be performed for the endpoint.
- If the conclusion is not upheld with the worst-case scenario approach, then the multiple imputation method will be used. A logistic regression model will be used and fifteen imputed datasets will be generated.
- Additionally a tipping point analysis will be performed. The proportion of missing values assigned the status of 'failure' will be sequentially increased to identify the point at which the study conclusions change (i.e., the null hypothesis is no longer rejected).

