7.5 SAFETY ANALYSES

7.5.1. Primary Safety Endpoint Analysis

The primary safety endpoint is evaluated on a per subject basis and will be calculated as the percent of all ITT subjects with sufficient follow-up that are free from all elements of the primary safety endpoint composite at 30 days. The primary safety hypothesis will be tested by calculating the lower one-sided 97.5% confidence limit, using the Exact method, for the rate of freedom from MAEs. If the lower limit exceeds the performance goal of 84%, the primary safety hypothesis will be met.

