Type E: Persistent luminal filling defect with delayed run-off of the contrast material in the distal lumen.

Type F: Filling defect accompanied by total coronary occlusion.

Embolization, Distal: Any distal emboli confirmed by imaging.

Embolization, Symptomatic: Clinical signs or symptoms of distal emboli detected in the treated limb distal to the treated lesion after the index procedure **or** noted angiographically and requiring mechanical or pharmacologic means to improve flow. This includes new abrupt occlusions or filling defects.

Enrollment: Subjects who are consented and meet all the study inclusion criteria and none of the study exclusion criteria and are treated or treatment is attempted with the study device will be considered enrolled into the study. Subjects who do not meet all inclusion and exclusion criteria (e.g., including ability to cross the lesion with a guidewire, target reference vessel diameter, patent tibioperoneal artery in the target limb, etc.) will be considered an angiographic screen failure and will not be followed in the study (no data will be collected on these subjects).

Hematoma: Collection of blood (or its degradation products) that exceeds 8 cm in diameter, requires treatment, or prolongs hospitalization.

Hypertension: Systolic BP >140 mmHg, or diastolic >90 mmHg requiring specific medical therapy.

Hypotension: Any prolonged systolic blood pressure <80 mmHg associated with symptoms and requiring intravenous vasopressor medications.

Infection, access site: Infection at the vascular access site, documented by lab culture or clinical evidence requiring medical treatment (irrigation, debridement, antibiotics, etc.) to resolve.

Infection, systemic: Systemic infection documented by positive lab culture or clinical evidence, requiring medical treatment to treat and resolve.

Intention to Treat (ITT): The principle of including outcomes of all subjects in the analysis who are enrolled and treated (attempted or completed) into the study, regardless of noncompliance, Protocol deviations, or withdrawal.

Limb Ischemia: Deficient supply of oxygenated blood to the tissues in the limbs that is due to obstruction of the inflow of arterial blood characterized by pain and/or discoloration of the limb and/or tissue loss.

Luminal Patency: Restenosis <50% as determined by angiography or duplex ultrasound.

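### Subjects aborted after device insertion belong to the ITT safety population but may leave at discharge, so their 30-day MAE status can go unrecorded (minor)

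*Combined protocol and SAP*

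**What the plan says.** **Who is in the population.** Section 4.8 treats a subject as enrolled once consent, eligibility and vascular access are in place and the study device is past the sheath. Section 7.2.2 puts all enrolled subjects in the ITT cohort: "The ITT Cohort will be the primary analysis population to determine if the primary safety endpoint was met in the study". Section 15 describes ITT as the principle of "including outcomes of all subjects in the analysis who are enrolled and treated (attempted or completed) into the study", regardless of withdrawal.

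**How long aborted subjects are followed.** Section 4.8 covers subjects whose "procedure was aborted without treatment with the device shall be followed through discharge for safety only and allowed to exit the study". Exit is permitted, not required.

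**Who counts at 30 days.** Section 7.3.1 sets the safety denominator as "the number of subjects who had sufficient follow up (at least 23 days for 30-day visit) plus any subjects who had an event" before the milestone visit. Section 7.5.1 agrees: the endpoint is "calculated as the percent of all ITT subjects with sufficient follow-up that are free from all elements" of the composite.

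**What is planned for missing data.** Section 7.3.1 lists worst-case, multiple-imputation and tipping-point analyses for the "potential impact of missing data on the primary effectiveness endpoint analyses, the following sensitivity analyses will be performed". The text shown has no counterpart for safety. It does promise: "All subjects will be accounted for in the study report, including the reasons for any subjects exiting the study early".

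**Events after exit.** Section 3.3 says: "The Investigator should follow all unresolved serious adverse events until the events are resolved", and it encourages an exit visit at the time of withdrawal. Sections 11.0 and 11.4 collect MAEs for as long as the study lasts, but neither provides for contact with a subject who has already left.

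**The concern.** Taken together, these rules let membership of the primary safety denominator depend on the outcome. An aborted subject with an MAE before discharge is in; one without an MAE who then exits is out. Whatever happens to the second subject between discharge and day 30 is unknown.

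These subjects were exposed to part of the system. Section 1.6.1 lists bleeding, embolism and venous flow disruption including DVT among the risks of the crossing device and snare, and several MAE components are of that kind. The two effects oppose each other: dropping event-free subjects lowers the observed freedom-from-MAE rate, while missing late MAEs raises it. In a single-arm comparison with a fixed goal, no control arm shares the loss.

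**Working it through.** **Inputs**
- Goal 84%, expected rate 92%, one-sided alpha 0.025, 169 evaluable, stated power 88% (7.1.2); exact lower limit (7.5.1).
- Enrollment 202 without roll-ins (4.3).
- Number aborted: an assumption. Section 1.5 offers two rough proxies from DETOUR I. First, 77 of 78 enrolled were treated: 202 × 1/78 = 2.6. Second, technical success was 98.8%, denominator not stated: 202 × 0.012 = 2.4. I use 2 to 3, with 10 (5%) as a stress case. Roll-ins, who are outside ITT (7.2.1), may absorb some early aborts.
- Unseen-MAE risk q after exit: an assumption, 2% to 8%. The upper end is the plan's whole expected 30-day risk (100% − 92%).
- All other subjects evaluable at 30 days, unless stated.

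**1. The plan's own figure.** For n = 169 the smallest r with P(X ≥ r | 0.84) ≤ 0.025 is 152 (attained alpha 0.0183). Power is P(X ≥ 152 | 0.92) = 86.9%, close to the stated 88%, so the test is understood correctly.

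**2. Cut-off.** The lower limit for x event-free of n is L = Beta⁻¹(0.025; x, n − x + 1), and the endpoint passes if L > 0.84. The most MAEs allowed is 21 for n = 195 to 202 and 20 for n = 188 to 194.

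**3. At the expected rate**

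| Aborted | Plan as written | Full status, no unseen MAE | Full status, all aborted had an MAE |
|---|---|---|---|
| 2 | 184/200 = 92.0%, L = 87.3% | 186/202 = 92.1%, L = 87.5% | 184/202 = 91.1%, L = 86.3% |
| 3 | 183/199 = 92.0%, L = 87.3% | 186/202 = 92.1%, L = 87.5% | 183/202 = 90.6%, L = 85.7% |

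The estimate moves by −1.4 to +0.1 points. The goal is met in every cell.

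**4. At the cut-off.** 179/200 (21 MAEs) gives L = 84.40% and passes. If one of the 2 aborted subjects had an unseen MAE, the full result is 180/202 (22 MAEs), L = 83.98%, which fails.

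**5. How often that happens.** Let E ~ Bin(202 − k, 0.08) be MAEs in the other subjects and U ~ Bin(k, q) the unseen MAEs. The plan passes while full status would fail when E ≤ 21 and E + U > 21. For k = 2 this is P(E = 21)·[1 − (1 − q)²] + P(E = 20)·q², with P(E = 21) = 0.0420 and P(E = 20) = 0.0564:
- q = 0.02: 0.0420 × 0.0396 + 0.0564 × 0.0004 = 0.0017
- q = 0.08: 0.0420 × 0.1536 + 0.0564 × 0.0064 = 0.0068

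For k = 3 the same calculation gives 0.0025 and 0.0101. The range is therefore 0.2% to 1.0%.

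**6. The other direction.** With 2 or 3 dropped from 202, n is 200 or 199 and the allowance stays at 21, so dropping event-free subjects alone cannot turn a pass into a fail. That depends on everyone else being evaluable. With other 30-day losses, one subject can matter: 174/195 (21 MAEs) gives L = 84.01% and passes, but dropping one event-free aborted subject gives 173/194, L = 83.93%, which fails.

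**7. Stress case.** With 10 aborted and q from 2% to 8%, the chance of a pass that full status would reverse is 0.1% to 1.2%; the chance of a fail that full status would reverse is 2.7% to 1.4%.

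**The case against.** The strongest reply is that this is a disclosed design choice with almost no effect. Section 7.5.1 states the follow-up restriction openly, 7.3.1 requires early exits and their reasons to be reported, and aborted subjects need not leave. If the ITT rate were exactly 84%, with 2 aborted subjects who are themselves 84% to 50% event-free, the type I error is 0.0175 to 0.024, against 0.0152 with full follow-up and still below 0.025. It exceeds 0.025 only with more aborts or a high risk after exit; for example, 3 aborted at 50% event-free gives 0.029. All of this stands and keeps the point minor. Disclosure, however, shows who left, not what happened to them.

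Stronger readings that the documents do not support:
- *The rule hides device harm.* In-hospital MAEs are counted as failures, and dropping event-free subjects works against the device. Nothing in the text fixes the net direction.
- *Section 7.1.2 removes these subjects because it starts the 30 days at stent graft implantation.* Section 4.8 sets Day 0 as the index procedure for every enrolled subject, and 4.2.2 and 6.1 count from the procedure. What remains is loose wording.
- *The Section 15 ITT definition is flatly contradicted.* It states a principle; 3.3 keeps data up to exit as appropriate, and 7.5.1 sets the estimator. That is tension, not contradiction.
- *Every failed attempt is plainly in ITT.* Section 15's enrollment definition counts attempted treatment, but it also makes failure to cross the lesion with a guidewire an example of an angiographic screen failure, with no data collected. Some failed attempts could be classed either way.
- *A replacement revascularization would be charged to the device.* The CD-TLR definition in Section 15 could be met, but event rules sit in a CEC charter (12.0) that is not shown.

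**Conclusion.** The gap is real and minor. Followed literally, 4.8, 7.2.2, 7.3.1 and 7.5.1 let inclusion in the primary safety denominator depend on whether an aborted subject had an early event. MAEs that begin after exit have no planned capture, and no safety sensitivity analysis in the text shown would reveal the effect.

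It is very unlikely to decide the trial: a 0.2% to 1.0% chance of a pass that full status would reverse, on the assumptions listed, with no change at the expected 92%. The abort count and the risk after exit are assumptions, and the result also depends on how complete 30-day follow-up is in everyone else. The case for acting is that the remedy is cheap and the information is hard to recover once subjects have left.

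**What to change.** 1. In 4.8, obtain 30-day MAE status for every enrolled subject, including aborted ones, before exit (by visit, or by telephone with record review), and include them all in the 7.5.1 denominator.
2. Repair the 4.8 sentence itself. It joins device insertion and an aborted procedure by an and/or, so read literally it also lets treated subjects leave at discharge.
3. Reconcile 4.8 with both Section 15 definitions (enrollment and ITT), so that a failed attempt after device insertion is clearly inside ITT and not a screen failure.
4. Confirm in the plan or the CEC charter how a replacement revascularization in an aborted subject is classified.
5. Align the time origin in 7.1.2 with Day 0 in 4.8 and with 4.2.2 and 6.1.
6. Optional and supportive only: for subjects whose 30-day status stays unknown, report the number of MAEs among them at which the conclusion would change.

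**Cost.** Wording changes and a 30-day contact for about 2 to 3 subjects (10 if 5% abort; both assumed). Event-free subjects who never received an implant enter as successes and dilute the implant risk slightly: 183/199 = 91.96% becomes 186/202 = 92.08%.
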